## 6.2 Description of Evaluations

Recalled assessments will be collected at four time points (baseline, mid-intervention, post-intervention, 4-week follow-up; Appendix F: Chart Review Form and Questionnaires) and a semi-structured interview conducted after completion of all assessments (either in person or by telephone; Appendix G: Semi-Structured Interview Guide). To minimize burden, all assessments via recalled questionnaires and interviews will be scheduled to coincide with the patients' appointment for chemotherapy.

Therefore, sequencing of each patient's assessments will be based on the timing of the respective patient's first completed chemotherapy visit. The standard chemotherapy timing is every two weeks. The randomized study condition will commence with the second chemotherapy visit. Given that there may be slight personal modifications to the standard schedule, we have proposed a design that will attempt to control for the possible effect of chemotherapy schedule on outcomes. If a chemotherapy visit is rescheduled for within two weeks of the standard schedule, the intervention will occur at that next visit (and all following assessments will then follow the subsequent standard chemotherapy schedule). If the rescheduled chemotherapy visit is more than two weeks later, the in-person study intervention session for that participant will not occur, the assessments will be mailed to the participant for completion, and this will be documented as an aspect of treatment fidelity.

Participants will also be asked to complete daily assessments of and adherence to home practice of both interventions for two weeks before and after the intervention via an automated daily survey and wear a wrist actigraphy device. Participants will also be asked to complete daily assessments of outcomes, mediators, adherence to home practice of the intervention for two weeks before and after the intervention via an automated daily survey (Appendix H: Daily Survey) and wear a wrist actigraphy device. Participants will be given the choice to respond to the automated daily diary via an interactive voice response system (IVRS) or internet survey hosted through a REDCap platform that will verify the date and time of assessments. IVRS and internet surveys have been successfully applied in similar research to assess daily symptoms in people with cancer and may improve compliance to assessments as compared to more commonly used paper daily diaries. Participants will be asked to complete surveys in the evening. Those who choose to complete the survey via IVRS will be called at approximately 6:00pm each evening (unless the participant indicates another strong time preference) and have the option to call back before they go to sleep. A paper guide with response options for the daily survey will be provided to improve comprehension over the telephone. If participants do not complete the first two surveys a STM will call them to confirm receipt of calls. If for any reason the automated survey system is not available, a STM will call the patient to complete the same survey. Participants will also be given a wrist actigraphy device and instructions for its use to measure circadian disruption. Instructions for use will be guided by [name] and [name].

Inflammatory cytokines will be collected via EDTA plasma samples by a Licensed Practical Nurse or phlebotomists along with patients regularly scheduled blood draws at weeks 2 and 10. Although this method may not account for possible variation in circadian patterns release of some cytokines, cytokines were similarly assayed in another study,

which associated elevated cytokines to increased fatigue during chemotherapy. All assays will be conducted by the Cytokine Core Laboratory led by [name].

Semi-structured interviews will be conducted face-to-face or by telephone and audio recorded by a trained facilitator for approximately 45 minutes. If the interview is implemented by telephone, no personal health information will be revealed unless speaking directly to the participant. Additional study process variables will also be tracked (e.g., recruitment, adherence to in-person intervention sessions, safety) and participants will be asked for feedback regarding reasons for declining participation and dropping out of the study.

## Measures

**Demographics.** Age, race/ethnicity, marital status, education level, ability to pay for the basics, alcohol/substance use and malnutrition status will be self-reported at baseline.

**Clinical Data.** Cancer type, chemotherapy regimen, stage of disease, recurrence status, receipt of other treatments, days since surgery, height, and weight will be abstracted from medical charts at baseline. Any chemotherapy dose modifications or symptoms related to dehydration (e.g., diarrhea) and medications for fatigue, sleep, anemia, depressive symptoms, and pain will be abstracted at follow-up.

## Questionnaire

- **Fatigue (recalled)** “in the past seven days” will be assessed with the 7-item measure of Fatigue from the Patient-Reported Outcomes Measurement Information System (PROMIS)-Cancer. Higher scores indicate more fatigue.
- **Depressive Symptoms (recalled)** will be assessed with the standadized10-item PROMIS-Cancer Depressive symptoms short-form.
- **Psychological Stress (recalled)** will be assessed by the 10-item Perceived Stress Scale (PSS). The PSS has 2 factors (stress and counter stress).
- **Regulation of Psychological Stress (recalled)** will be determined by ratings on four of the seven factors of the Cancer Behavior Inventory, which assess self-efficacy for stress management ( $\alpha = 0.86$ ), coping with treatment-related side-effects ( $\alpha = 0.82$ ), accepting cancer/maintaining positive attitude ( $\alpha = 0.86$ ), and affective regulation ( $\alpha = 0.81$ ).
- **Circadian disruption (recalled)** will be assessed with measures of activity and rest. Activity will be measured using the 3-item Godin's leisure score index (LSI), previously used with GI cancer patients during chemotherapy. Rest will be assessed with the 8-item PROMIS sleep disturbance short-form.
- **Efficacy Beliefs.** Participants will be asked after experiencing their assigned intervention how strongly they believe that it will improve their fatigue and depressive symptoms as implemented in another randomized controlled trial during chemotherapy with adapted items.
- **Outcome Expectancies (specific).** Using items adapted from other studies, participants will be asked how strongly they believe that various modalities

including moderate physical activity, gentle physical activity (e.g., stretching), a mind-body practice, writing, counseling or medication would improve their fatigue and mood during chemotherapy.

- **Outcome Expectancies (general).** Generalized outcome expectancies will be assessed by the Life Orientation Test-Revised.

### Daily Survey

- **Fatigue and Depressive Symptoms (daily)** “in the last day” will be assessed with 3 items selected from the PROMIS measures of fatigue and depression validated for use in daily diaries.
- **Psychological Stress (daily)** will be assessed with two items from the 4-item PSS that would be on the same factor to optimize internal consistency. The PSS has been successfully applied daily.
- **Regulation of Psychological Stress (daily)** will be assessed with the 3-item serenity subscale from the Positive and Negative Affect Schedule-Expanded Form.

**Actigraphy (Circadian Disruption - daily)** will be assessed with actigraphy, a non-intrusive alternative to the traditional polysomnogram when monitoring sleep in humans. The Actiwatch Spectrum model actigraph will be worn for two weeks at a time and uses an accelerometer to measure participant movement. This watch-like device has the ability to measure rest/activity patterns in a natural setting. Circadian disruption is defined as a ratio of nighttime activity to daytime activity with higher scores indicating greater circadian disruptions. A similar device and the same ratio has been used in patients during chemotherapy. Participants will also self-report their bedtimes and rising times using the daily automated survey to facilitate interpretation of actigraphy data.

**Treatment Fidelity.** Each in-person session will be documented with a checklist and 10% of these sessions will be observed to verify treatment fidelity.

**Intervention Home Practice.** Throughout the intervention, participants will keep daily paper logs of their home practice. In addition, one item will ask via the daily automated survey how many minutes participants practiced the intervention that day for two weeks after completion of the intervention as assessed in another yoga study.

**Adherence.** Percent of all assessments completed and the timeliness of completion will be tracked.

**Blood draws (Inflammation).** Inflammatory cytokines (i.e., IL-6, sTNF-R1, TNF- $\alpha$ ) that have been associated with fatigue during treatment for gastrointestinal cancer and influenced by yoga practice will be measured in plasma extracted from whole blood drawn during regularly scheduled clinical blood draws. All assays will be conducted by trained technicians in the Cytokine Core laboratory directed by [name]. IL-6 and TNF- $\alpha$  will be measured using high-sensitivity Quantikine® immunoassay kits (IL-6:

sensitivity=0.10 pg/ml, expected detection range=0-10.0 pg/ml; TNF-a : sensitivity=0.12 pg/mL, expected detection range=0-32.0 pg/ml). In our laboratory, the inter-assay and intra-assay CVs for IL-6 are 7.5% and 4.5%, respectively, and for TNF-a are 11.8% and 6.2%, respectively. IL-1Ra will be measured using standard Quantikine® kits (sensitivity=14 pg/ml, expected detection range=0-3000 pg/ml). All samples will be assayed in duplicate and the average of the two measures will be used for data analyses. To eliminate variability due to reagent conditions, we will pre-order the same lot number for all kits needed for a particular assay. In addition, we run all sample time points from individual participants on the same assay plate to reduce intra-assay variation. We will include an internal laboratory control on each 96-well plate. To date, inter-assay variability in this internal control has been low (CV<15%) in this laboratory, indicating that cytokine levels can be measured reliably over time. However, if the value for this control exceeds this 15% range, we will re-run the samples on that plate.

**Interview (Qualitative Feedback).** A semi-structured interview will also be implemented after all other data collection is complete to solicit feedback on the acceptability of data collection methods, the participants' experience with both the interventions (e.g., expected efficacy, what was useful), and barriers and facilitators to home practice.

### 6.2.1 Screening Evaluation

#### Consenting Procedure

If the patient is interested and referred by the physician, the PI or a STM will approach the patient at a clinic visit or call the patient at home to explain the protocol, answer questions, determine eligibility, and discuss informed consent (Appendix I: Recruitment Script; Appendix J: Recruitment Flyer). After making sure the patient clearly understands the study procedures and agrees to follow them, the patient will be asked to sign the informed consent form either in person or remotely. If signed remotely, patients will be asked to mail or fax the form back to us, as well as bring the original with them to their next clinic visit. If consent is obtained via REDCap, an original signature will be obtained at their next clinic visit. A copy of the consent form will be given to the participant in person the next time they are in clinic, and the original copy will be kept in the participant's file.

#### Screening

Screening evaluations will begin once a patient is scheduled for a consultation related to receiving first-line chemotherapy for GI cancers at VICC or CCC-WFU. The allowable range of time for screening is up to one year prior to study entry and baseline assessment. Electronic medical records of patients planning to receive chemotherapy will be reviewed by a STM to identify potential patients that meet enrollment criteria. This screening will consist of (Appendix K: Eligibility Checklist):

- Review of medical history
- Review of treatment plan

We will approach patients either in person or remotely (e.g., telephone, myWakeHealth) regarding their interest in study participation. For patients interested in the study, research staff will verify eligibility through patient interview regarding medical history.

### **6.2.2 Enrollment, Baseline, and/or Randomization**

#### **Enrollment**

Enrollment is defined as the randomization date or as the date all of the screening criteria are met and the individual agrees to participate. This enrollment date will be recorded (Appendix L: Protocol Registration Form).

#### **Registration Procedures**

All patients entered on any CCCWFU trial, whether treatment, companion, or cancer control trial, **must** be registered with the CCCWFU Protocol Registrar or entered into Oncology Research Information System (ORIS) Screening Log within 24 hours of Informed Consent. Patients **must** be registered prior to the initiation of treatment.

The following steps must be performed in order to ensure prompt registration:

1. Complete the Eligibility Checklist (Appendix K)
2. Complete the Protocol Registration Form (Appendix L)
3. Alert the Cancer Center registrar by phone, *and then* send the signed Informed Consent Form, Eligibility Checklist and Protocol Registration Form to the registrar, either by fax or e-mail.

\*Protocol Registration is open from 8:30 AM - 4:00 PM, Monday-Friday.

4. Fax/e-mail ALL eligibility source documents with registration. Patients **will not** be registered without all required supporting documents.

Note: If labs were performed at an outside institution, provide a printout of the results. Ensure that the most recent lab values are sent.

To complete the registration process, the Registrar will:

- assign a patient study number
- other appropriate actions
- register the patient on the study

#### **Baseline Assessments**

For participants who have successfully been screened for eligibility and are enrolled into the study, baseline assessments will be performed.

**Demographics.** Age, race/ethnicity, marital status, education level, ability to pay for the basics, alcohol/substance use and malnutrition status will be self-reported at baseline.

**Clinical Data.** Cancer type, chemotherapy regimen, stage of disease, recurrence status, receipt of other treatments, days since surgery, height, and weight will be abstracted from medical charts at baseline.

**Questionnaire:** Fatigue, Depressive Symptoms, Psychological Stress, Regulation of Psychological Stress, Circadian disruption, and Outcome Expectancies

**Daily Survey (weeks 0-2)** will assess baseline Fatigue and Depressive Symptoms (daily), Psychological Stress (daily), Regulation of Psychological Stress (daily), bedtimes and rising times

**Actigraphy (weeks 0-2)** will assess baseline circadian disruption (daily)

**Blood draws (Inflammation).** Inflammatory cytokines will be assessed at Week 2 prior to starting the intervention.

### **Randomization**

Randomization will occur the same day that screening is confirmed and will precede intervention initiation by approximately 2 weeks (corresponding with the timing between chemotherapy treatments 1 and 2).

#### **6.2.3 Blinding**

- Participants will be told that both groups offer programs to support their experience in coping with chemotherapy to match efficacy expectations.
- All STM will know to what arm participants are assigned. The STM collecting outcome assessments will not know which intervention each arm letter represents.
- A complete description of each study arm will be presented to participants upon their completion of all study measures (Appendix M: Thank You Letter).

#### **6.2.4 Followup Visits**

Adherence to all assessments completed will be tracked throughout the data collection period. In addition, the following treatment and followup visit assessments will be performed.

- *Weeks 2, 4, 6*
  - **Treatment fidelity** Each in-person session will be documented with a checklist.
  - **Intervention home practice.** Throughout the intervention, participants will keep daily paper logs of their home practice.
- *Week 8*

- **Treatment fidelity** the in-person session will be documented with a checklist.
- **Questionnaire:** Fatigue, Depressive Symptoms, Psychological Stress, Regulation of Psychological Stress, Circadian disruption and Efficacy Beliefs.
- **Daily survey (weeks 8-10)** will assess baseline Fatigue and Depressive Symptoms (daily), Psychological Stress (daily), Regulation of Psychological Stress (daily), bedtimes and rising times, how many minutes practiced the intervention that day.
- **Actigraphy (weeks 8-10)** will assess baseline circadian disruption (daily).
- *Week 10*
- **Questionnaire:** Fatigue, Depressive Symptoms, Psychological Stress, Regulation of Psychological Stress, Circadian disruption
- **Blood draws (Inflammation).** Inflammatory cytokines will be assessed.

#### 6.2.5 Completion/Final Evaluation

The following assessments will be performed the final visit (Week 14).

- **Clinical data.** Any chemotherapy dose modifications, symptoms related to dehydration (e.g., diarrhea) and prescription medications for fatigue, sleep, anemia, depressive symptoms, and pain will be abstracted at follow-up.
- **Questionnaire:** Fatigue, Depressive Symptoms, Psychological Stress, Regulation of Psychological Stress, Circadian disruption
- **Interview (Qualitative Feedback).** A semi-structured interview will be implemented after all other data collection is complete.

Participants who discontinue study the intervention early (e.g., due to changes in chemotherapy treatment location, who choose to withdraw participation) will require no specific evaluations. The reason for discontinuation will be documented. We will contact participants to obtain follow-up data remotely if they discontinue participation due to change in treatment location. Patients terminated from the study will undergo no further monitoring once they have stopped the study intervention.

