## **7.5 Follow-up for Adverse Events**

AEs will be monitored by the IMC and the PI for recurrences, resolution, and ongoing toxicities that may be related to the intervention. Documentation and reporting for follow-up AEs will occur according to reporting procedures described in Section 7.4. The duration for follow-up will be for the length of the study period while participants are enrolled in the study. If non-serious adverse events are related to the interventions, then the protocol will be modified to avoid adverse events. If the frequency of non-serious adverse events is higher than anticipated or alters the benefit risk ratio, the study investigators, after conferring with IMC, will also modify the protocol. Two or more specific adverse events among participants will prompt modification of the protocol.

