## **8. INTERVENTION DISCONTINUATION**

The intervention will be discontinued for a participant if: (1) the intervention is associated with an adverse effect for a specific participant (i.e., participant does not tolerate the intervention), (2) the participant no longer is interested or willing to receive the intervention or participate in the study, or (3) the participant's healthcare provider no longer recommends that the patient receive the intervention for medical reasons or (4) the participant no longer receives chemotherapy at designated research facility. The IMC and the principal investigator will review cases upon occurrence for discontinuation of intervention.

This study will be stopped prior to its completion if: (1) the intervention is associated with adverse effects that call into question the safety of the intervention; (2) difficulty in study recruitment or retention will significantly impact the ability to evaluate the study endpoints; (3) any new information becomes available during the trial that necessitates stopping the trial; or (4) other situations occur that might warrant stopping the trial. The PI will include an assessment of futility in the annual progress report to NIH and will consult with the study monitors to assess the impact of significant data loss due to problems in recruitment, retention, or data collection.

Participants will be followed with their permission if the study is discontinued. The duration of follow-up will be length of the proposed study. We will continue to document adverse events during the follow-up period.

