## 9.6 Data Analyses

SAS will be used for statistical analysis. Graphical and descriptive statistical methods will be applied to examine the shapes of study data distributions and need to transform, if necessary, for inferential analyses. Per descriptions above, analyses will be conducted using intention-to-treat principles as stated in the CONSORT 2010 guidelines and flexible protocol elements to minimize missing outcome data. Missing data are expected to be of two types: 1) nonrandom (death, deteriorating condition, or other lost-to-follow-up) and 2) random (inability to make it into the clinic for one of the assessment periods). Because fatigue post-intervention is the most critical outcome assessment point, the 1st assessment (study entry) and the post-intervention assessment point at Week 10 after study entry will be required for inclusion in the hypothesis testing analysis. Randomly missing assessments at Week 10 will be handled within the statistical analysis described. Randomly missing item responses within study measures will be handled according to the instructions for each instrument when developed and validated. Missing data assessments and drop-out occurrences will be analyzed to inform future research. We do not expect those types of missing data to be random; therefore imputation procedures will not be conducted. Maximum Type I error of 0.05 (uncorrected and/or corrected as necessary) will be maintained for statistical significance and all analyses will be performed in consultation with [name].

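### Section 6.2.5 does not separate stopping the intervention from leaving the study, so those who stop for reasons other than relocation have no planned Week 10 or Week 14 outcome

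*Combined protocol and SAP*

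**What the plan says.** **Early stopping (Section 6.2.5).** Participants who discontinue the intervention early "will require no specific evaluations". The examples given are a change of treatment location and a choice to withdraw. One exception follows: "We will contact participants to obtain follow-up data remotely if they discontinue participation due to change in treatment location". The paragraph ends by saying that patients terminated from the study "will undergo no further monitoring once they have stopped the study intervention".

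**Reasons for stopping (Section 8).** Four are listed: an adverse effect or intolerance, loss of interest or willingness, provider advice on medical grounds, and no longer receiving chemotherapy at the research facility.

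**Analysis (Sections 9.2, 9.5.1 and 9.6).** The primary outcome is recalled PROMIS fatigue at Week 10. The efficacy sample consists of those with both baseline and Week 10 data. Section 9.6 states that "analyses will be conducted using intention-to-treat principles as stated in the CONSORT 2010 guidelines". It classes death, deterioration and other loss to follow-up as non-random missingness and rules out imputation for it.

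**Adverse events (Section 7.5).** "AEs will be monitored by the IMC and the PI for recurrences, resolution, and ongoing toxicities that may be related to the intervention". The time limit is: "The duration for follow-up will be for the length of the study period while participants are enrolled in the study".

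**The concern.** Randomisation is at Week 0 and the four sessions run from Week 2 to Week 8, so anyone who gives up the sessions early does so before Week 10. If outcome collection lapses when the sessions stop, the analysed sample is selected after randomisation on tolerance, motivation and health. These may be related to fatigue and may differ between yoga and the attention control. The analysis sample is defined by having a Week 10 score, not by attending sessions. A participant who stopped but returned the questionnaire would therefore be included. It is Section 6.2.5 that leaves that score without a plan.

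Two of the plan's own aims are affected. Section 9.6 relies on flexible procedures to limit missing outcomes. Section 9.2 wants to understand how completers and non-completers differ, which for outcomes needs data on non-completers.

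Section 6.2.5 also leaves open what follow-up applies to a person whose intervention was stopped because of an adverse effect.

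**Working it through.** **1. Reasons for stopping against planned outcome collection**

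| Reason (Section 8) | Week 10 and 14 outcomes planned in 6.2.5? |
|---|---|
| Adverse effect or intolerance | No |
| No longer interested or willing | No |
| Provider advice | No |
| No longer treated at the research facility | Yes, remotely, when the treatment location changes |

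A related case is handled differently. Under Section 6.2, if chemotherapy is moved by more than two weeks, the session is skipped and the assessments are mailed. Missing a session does not by itself end assessment, but stopping the intervention may.

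**2. The plan's own precision figure**

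Inputs (Section 9.2): N = 44, 80% confidence, SD estimate no more than 10% below the true SD (14% by group). The 80% shortfall is 1 − √(χ²₀.₂₀(df)/df).

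- Pooled, df = 42: 9.8%; probability of being within 10% = 0.805.
- By group, n = 22, df = 21: 14.2%; probability of being within 14% = 0.795.

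Both figures reproduce. They use all 44 participants with no allowance for dropout.

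**3. Effect of the expected dropout on precision**

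Section 9.2 expects about 15% dropout: 0.15 × 44 = 6.6, about 7, leaving 37.

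- 37 analysed, df = 35: shortfall 10.8%; probability of being within 10% = 0.780.
- By group, 18 or 19 analysed: shortfall 16.0% or 15.5%.
- Standard error with all 44 relative to 37: √(37/44) = 0.917, so about 8% smaller. This is a ceiling.

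**4. Effect on the group contrast (illustrative)**

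Let p be the proportion missing in each arm and g the excess Week 10 fatigue of those missing over those observed. The completer mean understates the full arm mean by p × g, so the contrast shifts by (p_YST − p_AC) × g. The shift favours the arm with more dropout.

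The SD of 8 is from Section 9.2. The dropout splits (each averaging 15%) and g of 0.5 to 1 SD, that is 4 to 8 points, are assumptions that the documents do not supply.

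| Dropout, one arm v other | Shift, g = 4 | Shift, g = 8 |
|---|---|---|
| 15% v 15% | 0 | 0 |
| 20% v 10% | 0.10 × 4 = 0.4 | 0.10 × 8 = 0.8 |
| 25% v 5% | 0.20 × 4 = 0.8 | 0.20 × 8 = 1.6 |

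In SD units the non-zero shifts run from 0.4/8 = 0.05 to 1.6/8 = 0.20. The standard error of the difference with 18 v 19 analysed is 8 × √(1/18 + 1/19) ≈ 2.6 points, so they are about 0.15 to 0.6 of a standard error.

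**5. The adverse-event passages side by side**

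- Section 8 makes an adverse effect a reason to stop one participant's intervention and has the monitoring committee and principal investigator review such cases.
- Section 7.5 follows events for resolution, but only while the participant is enrolled.
- Section 6.2.5 ends monitoring for patients terminated from the study.
- Section 8 continues adverse-event documentation if the whole study is discontinued, and has no matching sentence for an individual stop.

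None of these says whether a participant stopped for an adverse effect is still enrolled.

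**The case against.** **The wording does not forbid collection.** Requiring no specific evaluations could mean only that there is no extra early-termination visit. This stands as far as it goes: a reader might infer that follow-up is barred, and the text does not say so. But nothing triggers contact either, except for those who relocate, and ad hoc contact in 44 people would itself be selective.

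**The plan wants completers.** Section 9.2 openly seeks effect sizes from those who complete the protocol. That is a stated choice, and collecting the questionnaires does not prevent that analysis. Whether the sample should be called intention-to-treat is a separate matter.

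**The model could cope.** Section 9.6 says that randomly missing Week 10 assessments are handled in the analysis, and Week 8 fatigue could in principle inform a sensitivity analysis. But Section 9.6 treats dropout as non-random and requires a Week 10 score for inclusion, and those who stop before Week 8 need not have a Week 8 score.

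**Not all 7 can be recovered.** Correct. Some will have died, deteriorated or withdrawn consent, and those who relocate are already contacted.

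**Remote collection is not fully specified.** Also correct. The documents describe mailing and unspecified remote contact. Telephone and REDCap completion are described for the daily survey, not for the Week 10 questionnaire.

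**Sections 6.2.5 and 7.5 contradict each other.** A reader might infer this, but the documents do not support it. The sentence ending monitoring concerns patients terminated from the study, and Section 7.5 is limited to enrolled participants, so the two can be read together.

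**Conclusion.** The concern holds as a gap in planned outcome collection. Participants who stop for intolerance, lost interest or provider advice, but would still answer a questionnaire, have no planned primary or Week 14 outcome. The analysis then leaves them out with no compensating method.

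The size is modest and uncertain. The loss of precision is small (shortfall 9.8% to 10.8% pooled), and no sample-size figure in the plan is wrong on this account. The shift of 0.4 to 1.6 points rests wholly on assumed dropout splits and excess fatigue. It is zero if both are equal across arms, so it shows what could happen and is not a forecast. The change is worth making because it is cheap and addresses selection that the plan itself expects to be non-random.

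The adverse-event issue is an ambiguity about who remains enrolled after stopping, not a direct contradiction.

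**What to change.** In Section 6.2.5, define stopping the intervention and withdrawing consent to follow-up as separate events. Ask everyone who stops the intervention, for whatever reason, to complete the Week 10 and Week 14 questionnaires remotely, for example by mail as Section 6.2 already does for rescheduled chemotherapy. End collection only when consent to follow-up is withdrawn. Record the date and reason for each event so that the completer analysis remains available.

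The cost is at most about 7 participants at two time points, fewer after deaths and consent withdrawals. One procedure needs wording. Section 7 describes the questionnaires as given in person except the follow-up, which may be mailed, and ties the suicide-item notification to receipt of the form. The plan must state how that existing notification applies to forms returned remotely.

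Separately, the sponsor must reconcile Sections 6.2.5, 7.5 and 8 by stating whether a participant stopped for an adverse effect remains enrolled and which adverse-event follow-up applies.
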